## List of abbreviation

EQ5D-5L	EuroQual 5 level generic quality of life measure
FABQ-A	Fear avoidance belief questionnaire activity
ICC	Intra-cluster correlation
ICD-PC	
ITT	Intention-to-treat
MI	Multiple imputation
NB	Negative binomial
Orebro-10	
PP	Per protocol
SAP	Statistical analysis plan
SPADI	Shoulder Pain and Disability Index

## 1.0 Introduction, study design and study objectives

### 1.1 Introduction

The confident shoulder study is a stepped wedge cluster randomized controlled trial that will assess the effectiveness of implementing an evidence-based guideline for shoulder pain in general practice in Norway. Detailed background information of this study are currently available in the study's protocol.

This statistical analysis plan (SAP) provides detailed description of the statistical analyses methods and techniques as outlined in the protocol. The description will also include the analysis population sample such as whether the research data will be analyzed on the basis of intention-to-treat (ITT) or per-protocol (PP). In addition, ways of dealing with missing data, which may cause data attrition and hence may affect the statistical power, are described. In particular, the focus will be given to multiple imputation of multilevel data.

### 1.2 Study design

A stepped wedge cluster randomized trial (SWCRT) with a focus on assessing the efficacy and feasibility of an evidence-based clinical guideline on shoulder pain management will be taken. The guideline, confident care will be delivered in sequential steps to each GP surgery (cluster) at a pre-determined time point and will be delivered to all the GP surgeries by the end of the study period. This two-year follow-up study will recruit 10 GP surgeries with each GP surgery initially acting as a control (usual care) until it crosses over to receive the confident care.

### 1.3 Primary and secondary objectives

The primary objective of the study is to assess whether implementing an evidence-based guideline for shoulder pain in general practice in Norway using an electronic decision tool will improve the patients' shoulder pain and function at 12 weeks compared to usual care.

The secondary objectives are to:

1. evaluate the feasibility of using an electronic decision support tool to implement the guideline

2. assess the health resource use and conduct a health economic evaluation of the treatment model

## **1.4 Hypotheses**

For the main research question, our hypotheses are

- Null hypothesis: Confident care of shoulder pain management does not give better clinical outcomes than usual care
- Alternative hypothesis: Confident care in shoulder pain management offers better clinical outcomes than the usual care.

The hypotheses of the secondary research question are

- Null hypothesis: Using an electronic decision support tool in the implementation of the guideline is not feasible
- Alternative hypothesis: Using an electronic decision support tool in the implementation of the guideline is feasible.

## **2.0 Sample size**

The primary outcome measure for the statistical power calculation is the yearly incidence rate of shoulder pain in general practice. Based on the ICD-PC codes for shoulder pain, approximately 67 patients on average are given a primary shoulder diagnosis in GP surgeries in Østfold County. Most of these GP surgeries have an average of three to four GPs. The incidence of shoulder pain in general practice has been reported to be 2-4%. Therefore, in estimating the sample size for this study, we used a conservative assumption of 3% as the incidence of shoulder pain diagnosis in this population. Setting the desired statistical power of the study at 80%, alpha at 0.05 and an intra-cluster correlation (ICC) of 0.002, we estimated that we needed to recruit 250 patients to detect a clinically important difference of 8 points between the groups, taking into account a possible dropout rate of 10%.

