#### 4.1 Primary outcome

The primary outcome measure is the Shoulder Pain and Disability Index (SPADI), which is a self-reported questionnaire with 13 items regarding shoulder pain and disability. These are patient level observations obtained at time points 0, 1, 2 and 3 denoting baseline, 6 weeks, 12 weeks and 52 weeks respectively.

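### The SAP sample size section names shoulder-pain incidence as the power endpoint although the target is an 8-point score difference, and its 80% power at 250 patients is not established for the stepped wedge

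*SAP*

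**What the plan says.** Section 2.0 opens the power calculation with an incidence endpoint: "The primary outcome measure for the statistical power calculation is the yearly incidence rate of shoulder pain in general practice". It cites about 67 patients with a primary shoulder diagnosis in the county's practices and a reported incidence of 2-4%, and continues: "we used a conservative assumption of 3% as the incidence of shoulder pain diagnosis in this population". It then lists 80% power, alpha 0.05, "an intra-cluster correlation (ICC) of 0.002" and 10% dropout, and concludes that "we needed to recruit 250 patients to detect a clinically important difference of 8 points between the groups".

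Other sections of the SAP describe a different endpoint and a specific design:

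- Section 4.1: "The primary outcome measure is the Shoulder Pain and Disability Index (SPADI"), measured at baseline and at 6, 12 and 52 weeks.
- Section 1.3: the primary objective concerns shoulder pain and function at 12 weeks.
- Section 1.2: the trial is a stepped wedge in 10 practices, each starting in usual care and crossing over in sequence.
- Section 6.1: Model 1 ignores time; Model 2 adds a time term.

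Section 2.0 names neither SPADI nor 12 weeks. It gives no SD, number of steps or periods, sidedness, formula or software.

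**The concern.** An incidence rate is not measured in points, so the endpoint named for the power calculation and the difference to be detected cannot belong to the same calculation. This is an incorrect statement in the SAP, not a detail left to the protocol.

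The stepped wedge matters as well. Later periods hold more exposed practices, so exposure is confounded with calendar time. Adjusting for period removes that confounding at a cost in precision. Section 2.0 does not say whether its 80% refers to an analysis with or without time.

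At stake is how the result is read. If the power of the planned analysis is in fact below 80%, a null finding could be taken as stronger evidence against an 8-point effect than the design can give.

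**Working it through.** **1. What the stated inputs can do.** A comparison of two means needs a difference, an SD, alpha, power and a clustering term. Section 2.0 supplies all but the SD. The 3% and the 67 have no place in the formula. As recruitment assumptions they are relevant, but there a lower incidence is the cautious choice. The value 3% is the midpoint of 2-4%; 2% would be the conservative one.

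**2. Trying to reproduce 250.** Evaluable patients: 250 × 0.9 = 225. With 225/10 = 22.5 per practice, the parallel-group design effect is 1 + 21.5 × 0.002 = 1.043. For a two-sided, two-arm comparison:

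N = 4 × (1.960 + 0.842)² × SD² / 8² × 1.043 / 0.9

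The SD is unknown, so the formula can only be solved backwards: SD = 8 × √(225/1.043/4) / 2.802 = 20.97. Put forward again, SD 21 gives 4 × 7.849 × 441/64 = 216, × 1.043 = 226, / 0.9 = 251. This shows which SD the formula would require, not which SD or formula was used.

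**3. The stepped wedge at the same size.** Assumptions: Hussey-Hughes variance with fixed period effects and a random practice effect; I = 10 practices spread evenly over S steps; T = S + 1 equal periods; 225 patients with one outcome each; ICC 0.002; two-sided 0.05. S is not in the SAP, so 2, 5 and 10 are tried.

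Var = I·s²·(s² + T·t²) / [(I·U − W)·s² + (U² + I·T·U − T·W − I·V)·t²]

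Here t² = ICC × SD², s² = (1 − ICC) × SD²/m, and m = 225/(10·T). U is the number of exposed practice-periods, W the sum of squared exposed counts by period, and V the same by practice.

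For S = 5 and SD 21:

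- m = 3.75, t² = 0.882, s² = 117.4
- U = 30, W = 220, V = 110
- Numerator: 10 × 117.4 × (117.4 + 6 × 0.882) ≈ 143,970
- Denominator: 80 × 117.4 + 280 × 0.882 ≈ 9,636
- Var ≈ 14.94, SE ≈ 3.87
- Power = Φ(8/3.87 − 1.96) ≈ 54%

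The SE is proportional to the SD, so the largest SD that keeps 80% is 21 × (8/2.802)/SE. One-sided, that limit is multiplied by 2.802/2.487 = 1.127.

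| Steps | SE at SD 21 | Power at SD 21 | Largest residual SD for 80%, two-sided | One-sided |
|---|---|---|---|---|
| 2 | 4.88 | 37% | 12.3 | 13.8 |
| 5 | 3.87 | 54% | 15.5 | 17.5 |
| 10 | 3.65 | 59% | 16.4 | 18.5 |

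**4. Sensitivity.** At SD 18 the two-sided power is 48%, 68% and 73% for 2, 5 and 10 steps. At SD 21 with ICC 0.05 it is 33%, 47% and 50%. Adjusting for baseline SPADI with an assumed correlation of 0.5 reduces SD 21 to 21 × √0.75 = 18.2 and gives 67% (5 steps) and 72% (10 steps). Reaching 80% at SD 21 would need a correlation of √(1 − (15.5/21)²) = 0.67 with 5 steps or √(1 − (16.4/21)²) = 0.62 with 10.

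All figures use a normal approximation. A small-sample correction for 10 clusters would lower them.

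**The case against.** The strongest reply is that the documents do not show the trial to be underpowered. A reader might infer from step 2 that 250 came from a parallel-arm formula and so does not suit this design. That is circular: SD 21 is obtained by assuming that formula, and other sample sizes could be made to fit it in the same way. The same 250 gives 80% power in a period-adjusted stepped wedge if the residual SD is about 12.3 to 16.4. The ICC shows that clustering was considered, and since no method is named, it cannot be said that the stepped wedge was ignored, only that it is not visible. This reply stands.

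Two further points stand in part. The SD, the steps and the period structure may be in the protocol, so their absence from the SAP is not itself an error; it only explains why 250 cannot be checked here. The illustration may also be pessimistic. It takes one outcome per patient, whereas the SAP plans four SPADI measurements and a patient-level random effect. It takes a two-sided test, whereas section 1.4 is worded in one direction: "Null hypothesis: Confident care of shoulder pain management does not give better clinical outcomes than usual care".

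None of this touches the endpoint contradiction or the misplaced incidence figures. It is also true that section 2.0 does not enter the analysis and that a null result should be judged by its confidence interval. The section nevertheless gives the stated basis for 80% power, and that basis is wrong as written.

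**Conclusion.** The point holds on the page: the power endpoint in section 2.0 contradicts both its own 8-point target and the SPADI primary outcome in section 4.1. The incidence figures belong to recruitment, and the 3% is not conservative there. The 80% power at 250 is not established for the stepped wedge, because the inputs given do not lead to 250 under any design.

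The size of any shortfall is conditional. Under the assumptions in the working, power is 80% or more only up to a residual SD of about 12.3, 15.5 or 16.4 for 2, 5 or 10 steps. At SD 21 it would be 37%, 54% or 59%. The SD, the number of steps and two-sided testing are assumptions that the SAP does not state, so these figures show what has to be settled and do not measure the trial's power. The documents support neither the conclusion that 250 is too few nor the conclusion that a parallel-arm formula was used.

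**What to change.** Revise section 2.0 as follows:

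- Name SPADI at 12 weeks as the endpoint of the power calculation, with 8 points as the difference on that score.
- Move the 3% incidence and the 67 patients to a separate sentence on recruitment feasibility, and drop the claim that 3% is conservative.
- State, or cite from the protocol, the SD and its source, the number of steps and periods, and the sidedness of the test.
- Recompute the power at 250 recruited (225 evaluable) with a period-adjusted stepped-wedge formula that reflects the planned baseline or repeated-measures adjustment, say which of the section 6.1 models it refers to, and restate the resulting power.

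Keep 250. The cost is new wording and one recalculation, with no extra patients and no change to the analysis models. The downside is that the stated power may become less favourable than 80%.

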### 3.0 Study populations

When analyzing the research data, we shall consider two populations; intention-to-treat (ITT) and per protocol (PP) to account for the fact that there may be delays between the expected start date and the actual start date. However, we expect all general practices to be randomized to receive the confident care guideline and implement it.

#### 3.1 Intention-to-treat (ITT) population

For the intention-to-treat analysis, a binary indicator variable, which denotes whether an observation occurred before or after randomization shall be constructed and used in the regression models. The binary factor shall represent the study months in each general practice pre-randomization and post-randomization. This means that in the ITT population, the general practices shall be analyzed according to their randomized crossover time regardless of whether this was achieved.

#### 3.2 Per Protocol (PP) population

In the per-protocol (PP) analysis, the effect of the confident care guideline shall be assessed by considering three categories in the regression analysis: 1. pre-randomization 2. post-randomization but pre-implementation and 3. post-implementation. This would allow adjustment due to delays in the implementation in the implementing general practices.

### 4.0 Outcomes

The research data for all patients diagnosed with shoulder pain will be collected from 10 general practices in Østfold County and in the health region of Helse Fonna. The outcomes will be obtained during the entire period of study between January 2020 and 2022 at all pre-specified time points. Therefore, multiple observations per patient are possible.

#### 4.1 Primary outcome

The primary outcome measure is the Shoulder Pain and Disability Index (SPADI), which is a self-reported questionnaire with 13 items regarding shoulder pain and disability. These are patient level observations obtained at time points 0, 1, 2 and 3 denoting baseline, 6 weeks, 12 weeks and 52 weeks respectively.

## 4.2 Secondary outcome

Several secondary outcome measures, also at patient level, shall be obtained. These will be measured either on four different measurement scales: Likert, ordinal, categorical (binary measures) and as counts.

The outcomes that will be measured on a Likert scale are

- EQ5D-5L (Health related quality of life) with scores ranging from 0 to 1.00
- Orebro-10 with scores ranging from 0 to 100
- Fear avoidance belief questionnaire activity (FABQ-A) with scores ranging from 0 to 24
- Pain self-efficacy Questionnaire with scores ranging from 0 to 60
- Brief Illness Perception Questionnaire (B-IPQ) with scores ranging from 0 to 90
- Patient experience Questionnaire with scores ranging from 17 to 88

The following secondary outcomes will be measured on an ordinal scale

- Participant global improvement
- Participant satisfaction with treatment

The binary outcomes to be categorized into (0/1) for (No/ Yes) will include the following secondary outcomes

- Work
- Work disability (sick leave)
- Medication usage such as over the counter pain medications, corticosteroid injections

Two count variables that we will consider are

- The number of sick leave days
- Medication usage frequency

With the exception of participant global improvement and participant satisfaction with treatment, all secondary outcomes will have baseline measurements.

## 5.0 Potential adjusting variables

The following demographic and baseline characteristics of the patients will be collected at the time of screening: patient age, gender, marital status, years of education and occupational status. Information about patients' comorbidities and other shoulder related information will be self-reported at baseline. These will include areas of bodily pain, previous shoulder pain, duration of shoulder pain and pain intensity.

We will also collect GPs demographic information such as age, gender, years since graduation, specialty, type of practice, number of GPs in the practice, the number of weekly working hours, and number of people on the GPs' lists at recruitment.

All results from the mixed effects binary logistic regression models shall be presented as estimated odds ratios with 95% CIs. For both linear and binary/ ordered mixed effects regression models, estimates of intra-cluster correlation (ICC), which describes the amount of variability in the outcome measures that can be attributed to differences between the general practices and the GPs within the general practices shall be obtained from the models. However, results from the count regression models shall be presented as incidence rate ratios (IRR) with their 95% CIs. For example, the IRR shall represent the **changes** in the number of sick day leave at a certain time point relative to the referent group. IRR estimates that are significantly above 1 shall represent significant increases in the number of sick leave days whereas IRR estimates that are significantly less than 1 shall represent significant decreases in the number of sick leave days.

We shall use descriptive statistics to summarize categorical data in the form of frequencies (counts) and percentages. Normally distributed continuous variables shall be summarized using the mean and standard deviation (SD) whereas non-normal continuous data shall be summarized using medians with first and third quartiles.

All analyses shall be performed using StataSE statistical package and the significance level shall be set at  $\alpha = 0.05$ .

## 6.1 Model building for the primary outcome

To explore the impact of the intervention on SPADI over time, we shall consider building the linear mixed effects regression models in four separate steps. We shall initially ignore the time effect in an unadjusted before and after the intervention model (model 1). Therefore, the SPADI for any given patient  $i$  seen by GP $_j$  in clinic $_k$  (general practice $_k$ ) is given as:

### Model 1

$$\text{SPADI}_{ijk} = \beta_0 + \beta_1 I_{ijk} + \alpha_{ijk} + \varepsilon_{ijk}$$

The parameter estimates  $\beta_0$  and  $\beta_1$  represent the fixed effects associated with the intercept and the effect of the intervention  $I$  (1 = exposed and 0 = unexposed (control)) for patient  $i$  seen by GP $_j$  in clinic  $k$ .  $\alpha_{ijk}$  is the random effect of patients nested by their GPs, who are in turn nested

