### Statistical Analysis Plan (SAP)

The confident shoulder study

in clinics and  $\varepsilon_{ijk}$  is the random error assumed to be homogeneous and uncorrelated with mean 0 and variance  $\delta^2$ .

### Model 2

To assess if any potential effect of the intervention on SPADI is also related to time, we shall introduce a time component  $T$  in model 2 and explore how the impact of the intervention develops over time.

$$\text{SPADI}_{ijk} = \beta_0 + \beta_1 I_{ijk} + \beta_2 T_t + \alpha_{ijk} + \varepsilon_{tijk}$$

Here, the parameter estimate  $\beta_2$  represents the effect of time.

### Model 3

Model adjustment of patient level characteristics presented in section 5 above shall be considered in model 3 as follows:

$$\text{SPADI}_{ijk} = \beta_0 + \beta_1 I_{ijk} + \beta_2 T_t + [\beta]X_{ijk} + \alpha_{ijk} + \varepsilon_{tijk},$$

where  $[\beta]$  is a matrix of the patient level covariates. The covariates that we shall consider include the following: patient age, gender, marital status, years of education and occupational status. In addition, GP level covariates such as age, gender, years since graduation, specialty, type of practice, number of GPs in the practice, the number of weekly working hours, and number of people on the GPs' lists at recruitment shall be considered for model adjustment by introducing an additional term,  $[\beta_1]X_{ijk}$  if necessary.

### Model 4

We also believe that the intervention may either decrease SPADI score over time as the GPs gain experience and are confident with the intervention or SPADI scores may increase over time if, for example, the GPs become less enthusiastic about it or if the intervention is not effective. Therefore, we will consider a two-way interaction between time and exposure to the intervention in model 4.

$$\text{SPADI}_{ijk} = \beta_0 + \beta_1 I_{ijk} + \beta_2 T_t + [\beta]X_{ijk} + \beta_3 T_t I_{ijk} + \alpha_{ijk} + \varepsilon_{tijk},$$

The parameter estimate  $\beta_3$  is the interaction between time and exposure to the intervention  $I$  (1 = exposure and 0 = control).

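### The primary objective is the SPADI difference at 12 weeks, but no coefficient in Models 1-4 is that difference and no model or contrast is named as primary

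*SAP*

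**What the plan says.** Section 1.3 sets the target, guideline care against usual care, as "shoulder pain and function at 12 weeks compared to usual care".

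Section 4.1 defines the primary outcome as SPADI, with "patient level observations obtained at time points 0, 1, 2 and 3 denoting baseline, 6 weeks, 12 weeks and 52 weeks respectively". Section 4.0 adds: "Therefore, multiple observations per patient are possible".

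Section 6.1 then states that "we shall consider building the linear mixed effects regression models in four separate steps":

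- **Model 1:** beta1·I, with time deliberately left out.
- **Model 2:** adds beta2·T.
- **Model 3:** adds patient covariates (age, gender, marital status, education, occupation) and, if needed, GP covariates. Baseline SPADI is in neither list, nor in section 5.
- **Model 4:** "we will consider a two-way interaction between time and exposure to the intervention in model 4", written as a single term beta3·T·I. The reason given is that GPs may grow more confident or less enthusiastic over time.

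Exposure is described in two ways. Section 3.1 builds the ITT indicator for each observation, according to whether it falls before or after the practice's randomised crossover. Section 6.0 repeats this in terms of study months. The equations in section 6.1 write I with patient, GP and clinic subscripts but no time subscript.

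Sections 3.0 and 6.0 call for both ITT and PP versions and rank neither.

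**The concern.** A plan whose objective is fixed at 12 weeks should name one number as the 12-week effect. Here beta1 in Models 1-3 is one exposure effect pooled over all rows in the outcome. Read literally, those rows include baseline, where no effect is expected, and 52 weeks, where the effect may differ. In Model 4, beta1 is the difference at T = 0 and beta3 is one slope. Neither is the 12-week difference.

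What the estimate means also depends on three things the SAP leaves open: what T measures, whether I can change within a patient, and whether baseline SPADI is a response or a covariate. The confirmatory test is therefore undefined, and an analyst could settle it after seeing the data.

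**Working it through.** **The plan's own figure.** Section 2.0 plans to "recruit 250 patients to detect a clinically important difference of 8 points between the groups", at 80% power, alpha 0.05, ICC 0.002 and 10% dropout. It gives no SD, so 250 cannot be checked directly. Back-solving with a two-sided alpha (assumed), a two-group comparison of means and the design effect 1 + (m − 1)·0.002:

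- SD 21 gives 218 patients before inflation.
- The design effect is 1.043 (m = 22.5) or 1.048 (m = 25), giving 227.4 or 228.5.
- Dropout, as ×1.1 or ÷0.9, brings this to 251-254.

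So 250 fits an SD of about 21. This is back-solved and does not bear on the point. Only the 8-point difference is used below.

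**Step 1: I fixed per patient (as the equations index it).** Assumptions: complete visits, no baseline difference, no calendar trend, covariates unrelated to I. Let d0, d6, d12, d52 be the true differences at the four visits.

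*Models 1-3:* beta1 = (d0 + d6 + d12 + d52)/4. For 0, 8, 8, 8 this is 24/4 = 6.0, or 25% below 8.

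*Model 4:* a least-squares line through the four differences.

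- T = 0, 1, 2, 3: mean T 1.5, mean difference 6, slope 12/5 = 2.4, intercept 6 − 1.5 × 2.4 = 2.4. At T = 2: 2.4 + 2 × 2.4 = 7.2.
- T = 0, 6, 12, 52: mean T 17.5, slope 140/1659 = 0.0844, intercept 4.52. At 12 weeks: 4.52 + 12 × 0.0844 = 5.5.

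The intercepts (2.4 and 4.5) appear as a baseline difference that does not exist.

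Other assumed patterns, all with 8 points at 12 weeks:

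| Differences at 0, 6, 12, 52 weeks | beta1, Models 1-3 | Model 4, beta1 + 2·beta3 (T = 0-3) |
|---|---|---|
| 0, 8, 8, 8 | 6.0 | 7.2 |
| 0, 4, 8, 8 | 5.0 | 6.4 |
| 0, 4, 8, 4 | 4.0 | 4.8 |
| 0, 8, 8, 0 | 4.0 | 4.0 |
| 0, 4, 8, 12 | 6.0 | 8.0 |
| 0, 8, 8, 16 | 8.0 | 10.4 |

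With d0 = 0, beta1 falls below d12 unless d6 + d52 is at least 3·d12.

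**Step 2: I set per observation (section 3.1).** No closed form applies, so a noise-free generalised least-squares fit was made on an assumed wedge:

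- 10 practices crossing in five steps of two (months 4, 8, 12, 16, 20) over 24 months, with even recruitment;
- visits after month 24 not observed;
- within-patient correlation 0.3 or 0.5;
- a true benefit of 8 at every follow-up visit for patients included after crossover.

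| Natural course of SPADI | Benefit in Model 1 | Benefit in Model 2 (T = visit) |
|---|---|---|
| Recovery 50, 40, 35, 25 | 9.5-11.3 | 0.9-2.1 |
| No recovery | 1.7-2.5 | 0.6-1.8 |

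Model 1 exaggerates under recovery because later visits more often fall after crossover, so ordinary improvement is credited to the guideline.

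**Step 3: T read as calendar time.** On the same wedge, with recovery and I fixed per patient, Model 2 with T as linear calendar time gives an apparent worsening of 7.4 to 9.8 points for a true benefit of 8. With T as visit it gives a benefit of 5.2-5.3. The meaning of T can thus decide the sign.

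**Step 4: visit-specific contrast.** With categorical visit, I × visit and I fixed per patient, the 12-week contrast returned 8.0 in every wedge scenario. Those scenarios had no calendar trend, so they do not test the period term proposed below. The need for that term follows from the design.

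**The case against.** **A reader might infer that the effect is always diluted.** The SAP does not support that. Dilution follows with I fixed per patient and effects that do not grow strongly after 12 weeks. The pattern 0, 8, 8, 16 gives 8.0 in Models 1-3 and 10.4 in Model 4. With I set per observation, Model 1 can overshoot.

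**A reader might infer that no 12-week effect can be obtained.** If T is the visit index, Model 4 contains one: beta1 + 2·beta3. It is exact when the effect is linear in the index and 10% low when the effect is constant from week 6. But the SAP never names this combination, and the reason given for Model 4, GPs gaining experience, suggests calendar time or time since crossover instead.

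**Linearity and baseline as a response are inferences.** The SAP never calls T continuous, and the labels 0-3 could be factor levels. Section 4.1 says when SPADI is collected, not which rows enter the model. This stands as a caution. Still, each time term carries a single coefficient, the residual in Models 2-4 carries a time subscript, and nothing removes baseline rows or adjusts for them. Model 1 has no time term, so linearity is not an issue there.

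**A smaller coefficient need not mean lost power.** That is right. Taking the standard error at one visit as 8/2.80 and multiplying by √((1 + 3ρ)/4) for four visits, beta1 under 0, 8, 8, 8 has power of 86%, 76% and 67% at assumed within-patient correlations ρ of 0.3, 0.5 and 0.7. The stated sample size does not depend on this point.

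**The models are steps in one build, not rival results.** This is partly fair: four models in two populations make at most eight results, and the steps are nested. But no step is named as the one that decides the trial.

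**Conclusion.** The concern holds as a mismatch between objective and analysis. The models as written contain no coefficient equal to the 12-week SPADI difference, and the SAP names no primary model or contrast. T, I and the handling of baseline are each open to more than one reading. This goes beyond missing detail, because section 6.1 writes the models out and they answer a different question from section 1.3.

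The direction of error is not fixed. For a true 12-week difference of 8, the worked cases with I fixed per patient and T as visit index run from 4.0 to 8.0 for beta1 in Models 1-3, and from 4.0 to 10.4 for the unnamed Model 4 combination. With I set per observation, Models 1 and 2 run from 0.6 to 11.3. The effect patterns, recovery curve, correlations and wedge layout are all assumptions. They show that the answer depends on choices the SAP has not made; they do not predict this trial's result. It should be settled before the analysis.

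**What to change.** Name one primary model in section 6.1, in the ITT population:

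- outcome: SPADI at 6, 12 and 52 weeks, with baseline SPADI as a covariate;
- follow-up visit as a categorical factor, with I × visit;
- a separate categorical calendar-period effect. In a stepped wedge exposure rises with calendar time, so without it the 12-week contrast would be confounded with secular trend;
- clinic, GP and patient random effects.

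Define I once per patient, from the practice's randomised crossover time relative to the patient's inclusion, and bring sections 3.1 and 6.0 into line. Define T explicitly, keeping follow-up visit and calendar period apart.

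State the I contrast at 12 weeks as the single primary estimate and test at alpha 0.05, and say whether the test is two-sided. The 6- and 52-week contrasts, Models 1-4 as now written and the PP analysis become supportive.

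The cost is SAP wording and a few degrees of freedom for the period terms. The outcome data and software stay the same.
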